Sponsor	Visterra Inc. [name]
Principal Investigator	Principal Investigator PAREXEL International Early Phase Clinical Unit-Los Angeles [name] USA [REDACTED]
Contract Research Organization	PAREXEL International Early Phase Clinical Unit – Los Angeles [name] USA
Adverse Event Reporting	PAREXEL Pharmacovigilance Safety Services [REDACTED]
Medical Monitor	PAREXEL International [name] USA [REDACTED]
Clinical Laboratory	GenX Laboratories GenX Laboratories Inc. [REDACTED]
Bioanalytical Laboratory (PK & ADA)	Syneos Health [REDACTED] [name] [REDACTED]

PROTOCOL SYNOPSIS

Protocol Title	A Phase 1, Randomized, Placebo-Controlled, Single Ascending Dose First-in-Human Study to Assess the Safety, Tolerability, Pharmacokinetics and Pharmacodynamics of VIS649 Administered Intravenously in Healthy Subjects
Study Numbers	[REDACTED] Sponsor Protocol No.: VIS649-101
Development Phase	Phase 1, safety and pharmacokinetics (PK)
Sponsor	Visterra Inc.
Principal Investigator	[REDACTED]
Study Center	PAREXEL Early Phase Clinical Unit–Los Angeles
Study Objectives	
Primary Objective: To evaluate the safety and tolerability of VIS649 in healthy subjects
 
Secondary Objectives:
 
• To characterize the PK profile of VIS649• To evaluate the effect of race on the pharmacokinetic profile of a single intravenously (IV) administered dose of VIS649 in healthy Japanese and non-Japanese subjects• To characterize the levels of anti-drug antibodies• To characterize the effect of VIS649 on pharmacodynamic (PD) parameters including:
○ changes in serum total IgA, IgG and IgM concentrations and time to recovery○ changes in whole blood circulating lymphocyte populations 
[REDACTED]
 
[REDACTED]
 
[REDACTED]

Study Design	
This is a phase 1, randomized, placebo-controlled, double-blind, single ascending dose study of IV VIS649 in healthy subjects.
 
Potential subjects will be carefully screened for eligibility prior to study enrollment. Randomization and blinding will occur according to a core randomization list administered by the site's unblinded pharmacist.
 
The study will enroll up to 45 subjects and will be conducted in four sequential dosing cohorts at four different dose levels (0.5, 2.0, 6.0 and 12 mg/kg), enrolling 9 subjects per cohort. Subjects will be randomized to VIS649 or placebo in a ratio of 7:2 (7 active, 2 placebo). Safety, PK and PD data from the initial cohorts will be assessed, to determine whether to initiate a fifth dosing cohort at a dose not to exceed 20 mg/kg.
 
Eligible subjects will report to the Clinical Pharmacology Unit (CPU) at study check-in (Day -1) and will be required to stay in the CPU until Day 2 (24 hours post infusion). On Day 1, a single dose of VIS649 or placebo will be administered IV in the morning after a light meal (as per the clinical unit standard). Pharmacokinetics sampling will occur on Day 1 starting with a collection prior to the start of infusion, at the end of infusion (60 minutes), and at 2 hours, 8 hours and 24 hours post end of infusion. Pharmacokinetics samples will also be drawn

	
on Days 3, 7, 14, 28, 42, 56, 70, and 112. Pharmacodynamics sampling (serum immunoglobulin levels) will occur at Baseline, Day 3 and weekly thereafter through the Week 8 visit, then once every two weeks through Week 16 (i.e., Weeks 10, 12, 14, and 16).
 
Sentinel subjects will be utilized; the first two subjects in each cohort will be randomized to receive either VIS649 (n=1) or placebo (n=1) and will receive study drug at least 24 hours before the remaining subjects in the cohort (7 subjects) are dosed. These 2 subjects shall remain confined to the study center for 24 hours after study drug administration.
 
The safety profile of these subjects over the 24 hour post-administration period will be reviewed to determine whether it is appropriate to proceed with enrollment of the remaining subjects in the cohort as planned. This will occur for each dose escalation. The remaining 7 subjects in each cohort will be randomized to receive VIS649 (n=6) or matched placebo (n=1).
 
The maximum duration of participation (Screening through End-of-study) for individual subjects will be approximately 20 weeks (5 months) with the possibility to extend up to 28 weeks (7 months). Each subject will participate in screening period lasting 1 to 28 days (0 to 4 weeks), an in-house stay for 2 to 3 days, and a post-administration period of 16 weeks. The scheduled final visit will occur 16 weeks post-dosing (112 days); however, two additional follow-up visits may be performed, at Weeks 20 and 24 post-dosing, if serum immunoglobulins have not returned to >lower limits of normal by the Week 16 visit or if emerging trial data suggest a value of later follow-up (i.e., for detection of anti-drug antibody responses).

Investigational Product	Medicinal
Number of Subjects	Up to 45 subjects may be enrolled. A total of 20 Japanese subjects (4 subjects per cohort) and 25 non-Japanese subjects (5 subjects per cohort) may be enrolled and randomized to receive a single dose of VIS649 or placebo. No more than one Japanese subject per cohort, may be randomized to receive placebo. Safety, PK and PD data from the initial four dosing cohorts will be assessed, to determine whether to initiate a fifth dosing cohort at a dose not to exceed 20 mg/kg.
Study Population	Healthy, non-smoking male and female subjects, 18 to 55 years of age with a body mass index between 18 and 32 kg/m ² , are planned for enrollment.
Criteria for Evaluation	
Safety Endpoints
 
The proportion of subjects with AEs and serious adverse events (SAEs) following administration of VIS649; safety will be assessed from the time of study drug administration to the end-of-study participation.
 
The following safety variables will be assessed from the time of study drug administration to the end-of-study participation:
 
• Adverse event assessments• Clinical laboratory tests (hematology, clinical chemistry and urinalysis)• Vital signs (sitting blood pressure, pulse, body temperature and respiratory rate),• Twelve-lead electrocardiogram (ECG)• Adjunctive procedures• Physical examination 
Secondary Endpoints
 
• Characterization of anti-drug antibodies (ADA) levels 
Pharmacokinetics Endpoints

	
The following pharmacokinetics parameters for VIS649 will be determined, as appropriate:
 
• C_{max}: Maximum serum VIS649 concentration determined directly from the concentration-time profile• T_{max}: Time of maximum serum VIS649 concentration determined directly from the concentration-time profile• $AUC_{0-\infty}$: Area under the concentration-time curve from pre-dose (time 0) extrapolated to infinite time 
• $t_{1/2}$: Apparent terminal elimination half life
 
• Vd: Apparent volume of distribution
 
• CL: Apparent clearance
 
Pharmacodynamics Endpoints
 
• Changes in total serum IgG, IgA and IgM concentrations and time to recovery• Changes in whole blood circulating lymphocyte populations
Statistical Methods	
Sample Size Considerations
 
As this is a first-in-human study and no clinical data are available, no formal sample size calculations have been performed. A total of up to 45 evaluable subjects is considered suitable to achieve the study objectives.
 
Data Presentation/Descriptive Statistics
 
In general, descriptive statistics for continuous variables will be summarized by treatment group using number of subjects, arithmetic mean, standard deviation, median, minimum and maximum; descriptive statistics for categorical data will be summarized by treatment group using frequency counts and percentages.
 
Summary of demographics and safety data will be analyzed using descriptive statistics as appropriate.
 
The VIS649 serum concentrations will be listed and summarized by dose and time-point. Individual and mean VIS649 concentration-time profiles will be plotted in linear and semi-log scales. Non-compartmental PK data analysis will be performed for VIS649 treated subjects to estimate the $AUC_{0-\infty}$, C_{max}, T_{max}, $t_{1/2}$, CL and Vd. Descriptive statistics for PK parameters will include number of observations, arithmetic mean, standard deviation, arithmetic coefficient of variation (%CV), and geometric mean, median, geometric %CV, minimum and maximum.
 
The number and percentage of subjects that are ADA positive will be summarized by dose. The impact of ADA on PK and the association with treatment-emergent adverse events and treatment-emergent serious adverse events will be assessed.
 
PD data will be assessed using change from baseline data and % change from baseline, as appropriate. The PK/PD relationship between investigational

	
medicinal product exposure and exploratory endpoints may also be analyzed by graphical displays if Sponsor requests.
 
All demographic, safety, PK, and PD data will be listed. Full details of the data analysis will be provided in a separate statistical analysis plan.

--	-----------------------------------------------------------------------------------------------------------------------------------------------------------------------------------------------------------------------------------------------------------------------------------------

TABLE OF CONTENTS

SIGNATURE PAGE	2
SIGNATURE PAGE	3
LIST OF STUDY STAFF.....	4
PROTOCOL SYNOPSIS.....	5
TABLE OF CONTENTS.....	9
List of Tables.....	12
List of Figures	13

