administered weekly over 4 weeks to groups of cynomolgus monkeys at doses of 0 (control), 0.5, 2.5, and 10 mg/kg, with an 8-week recovery observation period. Following treatment with 0.5 and 2.5 mg/kg doses, there was a [REDACTED] reduction from baseline in serum IgA levels. Monkeys treated with 10 mg/kg doses had a [REDACTED] reduction in serum IgA levels, similar to the effect observed in the prior study with 25 mg/kg dosing for 8 weeks, and thus providing evidence that APRIL inhibition does not completely suppress IgA production. Serum IgA level suppression was reversible, with a dose response in time-to-recovery during the 8-week follow-up period. The observation of a maximal suppressive effect of VIS649 on serum IgA levels [REDACTED] in monkeys was further supported in the third toxicology study, described below. There was a lesser effect of VIS649 on serum IgG levels [REDACTED] and IgM levels were not altered notably, in comparison with control animals. Peripheral blood lymphocyte counts were not significantly affected, including the following cell populations: T-lymphocytes (including T-helper and cytotoxic T-cell subsets), natural-killer cells, monocytes, and B-lymphocytes (including naïve, resting memory and activated memory B-lymphocyte subsets).

These studies led to the conduct of a United States Food and Drug Administration (US FDA) GLP-compliant 4-week repeat-dose IV toxicology study of VIS649 in cynomolgus monkeys, with a 20-week recovery period. Monkeys received weekly VIS649 injections for 4 weeks, at doses of 0 mg/kg (control), 25 mg/kg, 50 mg/kg, or 100 mg/kg.

VIS649-related reductions in total serum IgA levels were observed in all VIS649-treated animals [REDACTED] and the reductions were reversible as trends towards return to baseline were observed at all doses. All 3 dose levels demonstrated maximal pharmacologic effect that were consistent with previous studies in reduction in serum IgA and IgG levels with a minimal effect on IgM levels in VIS649 treated animals in comparison to the controls.

Serum IgG levels were moderately reduced [REDACTED] for a majority of animals at all timepoints. Serum IgM concentrations did not differ significantly between groups, including control animals.

There was no effect of VIS649 on measured plasma cytokine concentrations in the monkey toxicology studies (nor did VIS649 stimulate significant cytokine release in an *in vitro* human peripheral blood lymphocyte cytokine release assay).

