1.3. Risk-benefit Assessment

While VIS649 has not been evaluated in humans, the known effects of mAbs in humans suggest the following potential toxicities for single dose administration:

1. Infusion reactions: Anaphylaxis, fever, chills, rigors, nausea, vomiting, pain, headache, dizziness, shortness of breath, bronchospasm, hypotension, hypertension, pruritus, rash, urticaria, angioedema, diarrhea, tachycardia, and chest pain
2. Delayed allergic reactions: Serum sickness (i.e., urticaria, fever, general glandular enlargement, joint pains)
3. General: Injection site reaction

Mechanism based potential toxicities that might be anticipated based on VIS649 mechanism of action and preclinical studies include:

IgA suppression risks: VIS649 treatment is expected to reduce human IgA levels, with a predicted maximal reduction (with repeated dosing) to approximately 75% below baseline. In this single-ascending dose study, this degree of suppression is unlikely to be achieved, but it is anticipated that at least in the higher dose cohorts, IgA levels will be reduced below baseline, with effect persisting over weeks.

The normal range for serum IgA is approximately 70 to 400 mg/dL in adults [REDACTED]

[REDACTED]

[REDACTED]

Selective IgA deficiency (defined as persistently undetectable IgA, [REDACTED]) is the most common inherited immunodeficiency syndrome (occurring in about 1 in 500 Caucasian individuals). [3]. While this condition has heretofore been considered generally benign and is asymptomatic in the majority of patients, there is increasing recognition that selective IgA deficiency may be associated with recurrent sinopulmonary infection, allergy, autoimmunity and gastrointestinal microbiome perturbation [4, 5]. The risk for occurrence of these complications in the current study is low for multiple reasons: 1) IgA is expected to be suppressed, but not reduced to undetectable levels, 2) in this single dose-study, the effects on IgA levels are expected to be transient, and 3) the syndrome of selective IgA deficiency is often associated with additional immunologic impairments including T-cell disorders and common variable immunodeficiency syndrome.

IgG suppression risks: VIS649 is expected to have a moderate effect on serum IgG levels (with approximately 40% suppression-below-baseline nadir values predicted).

The normal range for serum IgG is approximately 600 to 1600 mg/dL in adults, [REDACTED]

[REDACTED]

[REDACTED]

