3.4. Stopping Criteria for the Clinical Study and Dose Escalation Criteria

If any of the dose limiting toxicities listed below are met, the relevant subject(s) data may be unblinded. If the toxicity is present in ≥ 1 subject randomized to active drug, then dose escalation will pause. Depending upon the nature of the event, a decision may be made to resume dosing, to proceed into the next cohort at a lower dose level, or to stop the study.

Based on safety criteria, the dose adjustment/stopping criteria are as follows:

- Adverse event stopping criteria:

- Any AE of severe intensity and related causality
 - Any SAE of related causality
- Vital sign stopping criteria:
 - Symptomatic hypotension (systolic blood pressure [SBP] <85 mmHg). If symptomatic hypotension that is related to the study drug is observed during the study, then a minimum of two repeat BP measurements should be obtained over a brief period. The mean of the three SBP measurements will be used to determine stopping criteria.
 - Tachycardia defined as heart rate >120 beats per minute (bpm) lasting longer than 30 minutes or with impaired consciousness
- Electrocardiogram stopping criteria:
 - QT interval [REDACTED] >500 msec (If a prolonged QTc interval is observed during the study, then a minimum of two repeat ECGs should be obtained over a brief period. The mean of the three ECGs will be used to determine stopping criteria.)
- Clinical laboratory stopping criteria:
 - Alanine aminotransferase (ALT) ≥3 times the upper limit of normal (ULN)
 - Aspartate aminotransferase (AST) ≥3 times the ULN
 - Serum creatinine >1.5 times the ULN
 - A decrease from Baseline in hemoglobin concentration >3 g/dL
 - White blood cell count <1,500/mm³
 - Platelets <50,000/mm³
 - Persistent serum IgA reduction to <15 mg/dL (with at least two measurements over at least one week apart) in ≥2 patients
 - Persistent serum IgA reduction to <7 mg/dL (or below local laboratory limit of detection) (with at least two measurements, at least one week apart) in any single patient
 - Persistent serum IgG reduction to <300 mg/dL (with at least two measurements, at least one week apart) in ≥2 patients
 - Persistent serum IgM reduction to <25 mg/dL (with at least two measurements, at least one week apart) in ≥2 patients.

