6.2.1.1.3. Adverse Events of Special Interest

An adverse event of special interest (serious or non-serious) is one of scientific and medical concern specific to the Sponsor's product or program, for which ongoing monitoring and rapid communication by the Principal Investigator to the Sponsor can be appropriate. Such an event might warrant further investigation in order to characterize and understand it. Depending on the nature of the event, rapid communication by the Sponsor to other parties might also be warranted.

Examples of these are all AEs of

- Infusion reactions: Fever, chills, rigors, nausea, vomiting, pain, headache, dizziness, shortness of breath, bronchospasm, hypotension, hypertension, pruritus, rash, urticaria, angioedema, diarrhea, tachycardia, and chest pain
- Delayed allergic reactions: Serum sickness (i.e., urticaria, fever, general glandular enlargement, joint pains)
- General: Injection site reaction
- Any documented infection

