recorded within 30 minutes prior to the start of the infusion, then every 15 minutes until the infusion is complete and post infusion at 60 minutes, 2 hours and 4 hours. On subsequent visits, vital signs will be recorded, as possible, at approximately the same time of day, if convenient.

4. On Day 1 electrocardiograms will be done within 30 minutes prior to infusion and at the end of the infusion (+10 min).
5. On the day of study infusion (Day 1), blood samples for PK analysis will be collected prior to start of the infusion, at the end of infusion (60 minutes), and at 2 hours, 8 hours, and 24 hours post end of infusion. All subjects will have PK samples drawn on Days 3, 7, and Weeks 2 (Day 14), 4 (Day 28), 6 (Day 42), 8 (Day 56), 10 (Day 70), and 16 (Day 112).
[REDACTED]
7. Follow-up visits may be performed if serum immunoglobulin levels or lymphocytes have not returned to > lower limits of normal or if emerging trial data suggest a value of later follow-up (i.e. for ADA responses)

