9. ETHICAL, LEGAL AND ADMINISTRATIVE ASPECTS

9.1. Data Quality Assurance

The monitoring of the study will be conducted under the responsibility of the Sponsor by the CRO. The monitor will perform on-site and/or remote monitoring visits as frequently as necessary per the individual study monitoring plan.

The Principal Investigator must prepare and maintain adequate and accurate records of all observations and other data pertinent to the clinical study for each study participant. Frequent communication between the clinical site and the Sponsor is essential to ensure that the safety of the study is monitored adequately. The Principal Investigator will make all appropriate safety assessments on an ongoing basis. The Medical Monitor may review safety information as it becomes available throughout the study.

All aspects of the study will be carefully monitored with respect to Good Clinical Practice (GCP) and SOPs for compliance with applicable government regulations. The Study Monitor will be an authorized individual designated by the Sponsor. The Study Monitor will have access to all records necessary to ensure integrity of the data and will periodically review the progress of the study with the Principal Investigator. The Sponsor will be entitled to audit the facilities used in the clinical and laboratory parts of the study, as well as to access all the data files pertaining to the study. Similar procedures may also be conducted by agents of any regulatory body, either as part of the a national GCP compliance program or to review the results of this study in support of a regulatory submission. The Investigator should immediately notify the Sponsor if they have been contacted by a regulatory/ethics agency concerning an inspection.

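### The sentinel go/no-go rests on a 24-hour safety profile, but no vital signs are scheduled between 4 h post infusion and Day 3, and no temperature is scheduled after dosing

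*Protocol*

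**What the plan says.** The protocol Synopsis (Study Design) sets the sentinel rule: "The safety profile of these subjects over the 24 hour post-administration period will be reviewed to determine whether it is appropriate to proceed" with the remaining seven subjects of the cohort. Of those seven, six receive VIS649 and one placebo. SAP section 3.1 keeps sentinels for cohorts 1-4 and drops them for its cohort 5.

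Protocol Table 9 (section 7.1) marks vital signs on Day 1, leaves Day 2 empty and marks Day 3 (+1 day). Footnote 3 gives the Day 1 times as one pre-infusion set, "then every 15 minutes until the infusion is complete and post infusion at 60 minutes, 2 hours and 4 hours". It confines vital signs after Screening to blood pressure, heart rate and respiratory rate. SAP Table 1 has the same empty Day 2 cell, and its footnote 3 allows temperature on Day -1 and before dosing on Day 1, but not afterwards.

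Footnote 5 already has staff drawing PK blood "at the end of infusion (60 minutes), and at 2 hours, 8 hours, and 24 hours post end of infusion".

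Section 3.4 lists among its vital-sign stopping criteria: "Tachycardia defined as heart rate >120 beats per minute (bpm) lasting longer than 30 minutes or with impaired consciousness". Section 1.3 opens its list of expected antibody toxicities with "Infusion reactions: Anaphylaxis, fever, chills, rigors, nausea, vomiting, pain, headache, dizziness, shortness of breath, bronchospasm, hypotension, hypertension". Section 6.2.1.1.3 makes the same group of events adverse events of special interest: "Infusion reactions: Fever, chills, rigors, nausea, vomiting, pain, headache, dizziness, shortness of breath".

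**The concern.** The go/no-go is meant to use a full 24 hours of safety information, but the scheduled vital signs cover only the first few hours.

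Two consequences follow. First, the heart-rate criterion in section 3.4 can be met without symptoms, so only a measurement can trigger it. After 4 h none is scheduled in the single active sentinel before six more subjects receive the same dose. Second, a mild fever has no scheduled reading at any time after dosing, although the protocol twice names fever as an event to watch for.

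Within a cohort, the sentinel review is the only check between the first active subject and the next six. The Safety Monitoring Committee's review of vital signs comes at Day 14 or Day 28, after all nine subjects have been dosed. It protects the next cohort, not this one.

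**Working it through.** The plan gives no figure to reproduce. The check is a reading of the schedule followed by subtraction.

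**Is the Day 2 blank real?** Tables read from a PDF can lose alignment, so other rows were used as a control. Up to Week 1 of protocol Table 9:

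| Row | Marked at |
|---|---|
| Vital signs | Screening, Baseline, D1, D3, W1 |
| AE check | Baseline, D1, D2, D3, W1 |
| PK sampling | D1, D2, D3, W1 |
| ECG | Screening, Baseline, D1 |
| Chemistry/coagulation | Screening, Baseline, D3 |
| Brief physical examination | D3 |

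The AE and PK rows carry a Day 2 mark and the vital-signs row does not. The vital-signs and AE rows of SAP Table 1 show the same pattern, and footnote 3 independently stops at 4 h. Day 2 therefore holds only the AE check and the 24 h PK sample. Footnote 1 delays discharge until the 24-hour procedures are done, but no vital signs are among them.

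**Sets currently in the window** (1-hour infusion, section 5.6):
- during infusion, at 15, 30, 45 and 60 min: 4
- after infusion, at 60 min, 2 h and 4 h: 3
- total: 4 + 3 = 7, the last at 4 h after the end, which is 1 + 4 = 5 h after the start

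**Uncovered part of the 24 hours:**
- from end of infusion: 24 − 4 = 20 h; 20/24 = 83%
- from start of infusion: 24 − 5 = 19 h; 19/24 = 79%

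If Day 3 is taken as 48 h after the start of dosing (an assumption), the wait to the next scheduled set is 48 − 5 = 43 h, or 72 − 5 = 67 h at the end of the +1 day window.

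**Scheduled post-dose temperatures:** 0 in both documents.

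**Subjects dosed after a sentinel decision:**
- cohorts 1-4: 7 × 4 = 28 (6 × 4 = 24 active, 4 placebo)
- with this protocol's optional cohort 5: 7 × 5 = 35 (30 active, 5 placebo)

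**With sets added at 8 h and 24 h post infusion:**
- unmeasured stretches: 8 − 4 = 4 h and 24 − 8 = 16 h, so the longest falls from 20 h to 16 h
- post-dose temperatures per subject, at 60 min, 2 h, 4 h, 8 h and 24 h: 5

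**The case against.** The best case for the plan is that the sentinel step looks for acute clinical reactions, and measurement is densest when those are expected. Sentinels are confined for 24 hours, staff see them at the 8 h and 24 h draws, an AE check falls on Day 2, and section 9.1 adds: "The Principal Investigator will make all appropriate safety assessments on an ongoing basis". Preclinical data are reassuring: "There was no effect of VIS649 on measured plasma cytokine concentrations in the monkey toxicology studies" (section 1.1). All of this stands. It is why the concern is limited to silent or mild changes of low likelihood. It does not guarantee a reading in a subject who feels well.

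Second, protocol sections 3.2.1 and 6.2.3 and the Synopsis name temperature as a safety variable, so zero post-dose readings might be only a drafting conflict. But these texts give no post-dose clock times, and section 6.2.3 refers to Table 9, whose footnote 3 excludes temperature after Screening. The conflict is a further reason to correct the footnote.

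Third, section 3.4 governs pauses in escalation and is not written as the sentinel rule. It has no temperature criterion, and two spot readings would miss many transient tachycardias. These are fair limits. The added readings would inform the sentinel judgement; they would not provide continuous surveillance, and 16 hours overnight would remain unmeasured.

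Fourth, the silent laboratory criteria also have no reading before Day 3. That is true, but vital signs take minutes at visits already scheduled and acute changes show in them.

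Finally, a Safety Management Plan is mentioned but not available here. It may contain more detail on the sentinel review.

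**Conclusion.** The concern holds. The sentinel decision is based on 24 hours, and scheduled vital signs stop after the first 4 (from end of infusion) or 5 (from start), leaving 20 of 24 h (83%) or 19 of 24 h (79%) without a set. No temperature is scheduled after dosing in either document.

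The conclusion rests on the Day 2 cell being truly blank. Both tables, the marked AE and PK rows and footnote 3 support that. It also assumes that unscheduled, clinically prompted measurements, which nothing forbids, cannot be relied on in a subject without symptoms.

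The counts of 28 and 35 are headcounts behind the decision, not estimates of risk. No endpoint or analysis is affected. This is an inexpensive safety improvement to a first-in-human design; it does not undermine the study.

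**What to change.** In protocol Table 9 and footnote 3:

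1. Add a set of blood pressure, heart rate, respiratory rate and temperature at the existing 8 h and 24 h post-infusion PK draws. Repeat after 30 minutes if heart rate exceeds 120 bpm, so that the section 3.4 criterion can be applied.
2. Add temperature to the existing 60 min, 2 h and 4 h post-infusion sets.

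In the sentinel paragraph, state that the sentinels' vital signs through 24 h are reviewed before the remaining seven subjects are dosed and before the sentinels are discharged. Mirror the table change in SAP Table 1 for consistency.

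Cost:
- new sets: 2 × 36 = 72 over cohorts 1-4, of which 2 × 8 = 16 are in sentinels; restricting them to sentinels would leave those 16
- with this protocol's optional cohort 5: 2 × 45 = 90 (2 × 10 = 20 in sentinels); under the SAP's 51 subjects: 2 × 51 = 102
- added temperatures at existing sets: 3 × 36 = 108
- delay: 24 h after the end of a 1-hour infusion is 25 h after its start, so the remaining subjects could wait about 1 h beyond the 24 h minimum
- some incidental out-of-range readings in healthy subjects will need repeating

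The 8 h to 24 h interval would still depend on confinement and AE checks.
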